15. STUDY MEDICATION COMPLIANCE

Unless otherwise specified, the study medication compliance summary tables will include the following columns: SEP-363856 50 to 100 mg/day, Quetiapine XR 400 to 800 mg/day, and Total.

Compliance to study medication will be presented for the SAF population, by the actual treatment group.

Percent compliance will be calculated overall for the double-blind treatment period. Non-compliance is defined as less than 75% or more than 125% non-missing compliance for the double-blind treatment period. Subjects with missing compliance will not be classified as non-compliant. Compliance will be summarized both as a continuous variable and categorically (i.e. number and percentage of subjects with compliance <75%, 75% - 125%, >125%, and missing).

15.1. DERIVATIONS

Overall Compliance (%) to study medication in percentage will be calculated as follows:

$$\frac{\sum(\# \text{ Capsules Dispensed for Visit } j - \# \text{ Capsules Returned for Visit } j - \# \text{ Capsules Lost for Visit } j)}{\# \text{ Capsules should be taken per day} \times \text{Duration of Exposure}} \times 100\%$$

If the number of capsules dispensed, returned, and/or lost as collected on the "Study Drug Administration / Drug Accountability" CRF form is missing for one or more visits, the overall compliance will be calculated based on visits with complete drug accountability data available. That is, the numerator of the formula above will only include visits with the number of tablets dispensed, returned, and lost available, and the denominator should be adjusted to exclude dosing periods covered by visits excluded from the calculation (i.e., change "Duration of Exposure" to be Duration of Exposure – dosing periods [sum of (EXENDTC – EXSTDTC+1)] covered by visits with missing or incomplete accountability data).

16. EFFICACY OUTCOMES

Unless otherwise specified, the efficacy analysis and summary tables will include the following columns:

Document: CCI

Author: PPD

Version Number: 0.6

Version Date: 30JAN2023

Template No.: CS_TP_BS016 Revision 6

Reference: CS_WI_BS005

Effective Date: 02Dec2019

SEP-363856 50 to 100 mg/day, Quetiapine XR 400 to 800 mg/day.

All analyses of the efficacy variables will be based on the EFF population and, for selected variables/analyses, the PP population by the randomized treatment group.

Efficacy data collected after an emergency treatment unblinding (see protocol Section 7.2.3) will not be used in any statistical analysis. These data will be listed in data listings only.

16.1. PANSS

The PANSS (Positive and Negative Syndrome Scale) is an interview-based measure of the severity of psychopathology in adults with psychotic disorders and comprises 30 items and 3 subscales. The positive subscale assesses hallucinations, delusions, and related symptoms (7 items); the negative subscale assesses emotional withdrawal, lack of motivation, and related symptoms (7 items); and the general psychopathology subscale assesses other symptoms such as anxiety, somatic concern, and disorientation (16 items). An anchored Likert scale from 1 to 7 (1 = absent, 7 = extreme, with values of 2 and above indicating the presence of progressively more severe symptoms) is used to score each item.

Individual items are summed to derive the following scores:

- Total score = sum of all 30 items. Total score ranges from 30 to 210.
- Subscale scores = sum of items within each of the following subscales:
 - Positive subscale: delusions, conceptual disorganization, hallucinatory behavior, excitement, grandiosity, suspiciousness/persecution, hostility. The subscale score ranges from 7 to 49.
 - Negative subscale: blunted affect, emotional withdrawal, poor rapport, passive/apathetic social withdrawal, difficulty in abstract thinking, lack of spontaneity and flow of conversation, stereotyped thinking. This subscale score ranges from 7 to 49.
 - General psychopathology subscale: somatic concern, anxiety, guilt feelings, tensions, mannerisms and posturing, depression, motor retardation, uncooperativeness, unusual thought content, disorientation, poor attention, lack of judgment and insight, disturbance of volition, poor impulse control, preoccupation, active social avoidance. This subscale score ranges from 16 to 112.

Document: CCI

Author: PPD

Version Number: 0.6

Version Date: 30JAN2023

Template No.: CS_TP_BS016 Revision 6

Reference: CS_WI_BS005

Effective Date: 02Dec2019

- Marder factor scores = sum of items within each of the following factors (Marder, Davis, Chouinard. 1997):
 - Negative symptoms: blunted affect, emotional withdrawal, poor rapport, passive/apathetic social withdrawal, lack of spontaneity and flow of conversation, motor retardation, active social avoidance. This Marder factor score ranges from 7 to 49.
 - Positive symptoms: delusions, hallucinatory behavior, grandiosity, suspiciousness/persecution, stereotyped thinking, somatic concern, unusual thought content, lack of judgment and insight. This Marder factor score ranges from 8 to 56.
 - Disorganized thought: conceptual disorganization, difficulty in abstract thinking, mannerisms and posturing, poor attention, disturbance of volition, preoccupation, disorientation. This Marder factor score ranges from 7 to 49.
 - Uncontrolled hostility/excitement: excitement, hostility, uncooperativeness, poor impulse control. This Marder factor score ranges from 4 to 28.
 - Anxiety/depression: anxiety, guilt feelings, tension, depression. This Marder factor score ranges from 4 to 28.
- UPSM (Uncorrelated PANSS Score Matrix) factor scores = PANSS item scores of each subject at each visit transformed using the UPSM to obtain scores of 7 transformed PANSS factors (Hopkins et al. 2018):
 - POS: Positive
 - DIS: Disorganized
 - NAA: Negative apathy/avolition
 - NDE: Negative deficit of expression
 - HOS: Hostility
 - ANX: Anxiety
 - DEP: Depression

Document: CCI

Author: PPD

Version Number: 0.6

Version Date: 30JAN2023

Template No.: CS_TP_BS016 Revision 6

Reference: CS_WI_BS005

Effective Date: 02Dec2019

- The transformation will be done as follows:

$$[\text{Transformed PANSS Factor Data}]_{(N \times 7)} = [\text{PANSS Data}]_{(N \times 30)} * [\text{UPSM}]_{(30 \times 7)}$$

where

- $[\text{Transformed PANSS Factor Data}]_{(N \times 7)}$ is the transformed matrix with N sets of scores for the 7 transformed PANSS factors.
- $[\text{PANSS Data}]_{(N \times 30)}$ is a matrix with N PANSS assessments and 30 columns containing the scores of 30 PANSS items ordered in the same way as shown in UPSM.
- $[\text{UPSM}]_{(30 \times 7)}$ is a matrix with 30 rows (one for each PANSS item) and 7 columns (one for each of the 7 transformed PANSS factors). This matrix is presented in [APPENDIX 5](#).

- UPSM total factor score = sum of the 7 UPSM factor scores.

PANSS is assessed at these study visits: Visit 1, Visit 2, Visit 3, Visit 5, Visit 6, Visit 8, Visit 10, Visit 12, Visit 14, Visit 16, and Visit 17.

16.1.1. OBSERVED VALUES AND CHANGE FROM BASELINE IN PANSS TOTAL SCORE

16.1.1.1. Exploratory Analysis of PANSS Total Score

Data will be analyzed using a mixed model for repeated measures (MMRM) under the MAR assumption. Under this assumption, the efficacy outcome of subjects in each treatment group after early discontinuation will exhibit the same future evolution as subjects in the same group remaining in the study. The MMRM model will include fixed factors for treatment, visit (Weeks 1, 4, 8, 16, 24, 32, 40, 48, 52; as a categorical variable), country, and treatment-by-visit interaction and include Baseline PANSS total score as a covariate. An unstructured covariance matrix will be used to model the within-subject correlation. Kenward-Roger approximation will be used to calculate the denominator degrees of freedom.

The least squares (LS) mean difference in PANSS total score change from Baseline at Week 52 (SEP-363856 group vs. Quetiapine), their standard errors, the two-sided 95% CIs, and the associated nominal p-values will be calculated from the MMRM model.

In addition, the following statistics will be reported in the MMRM table:

Document: CCI

Author: PPD

Version Number: 0.6

Version Date: 30JAN2023

Template No.: CS_TP_BS016 Revision 6

Reference: CS_WI_BS005

Effective Date: 02Dec2019

- The LS mean difference in PANSS total score change from Baseline at Weeks 1, 4, 8, 16, 24, 32, 40, 48; their standard errors; the two-sided 95% CIs; and the associated nominal p-values.
- The LS mean of PANSS total score change from Baseline at each time point for each treatment group, their standard errors, and the two-sided 95% CIs.
- Within group effect size at each time point, calculated as the LS mean of each treatment group at each time point divided by the model estimate of standard deviation, obtained as the square root of the corresponding diagonal element of the residual covariance matrix (R matrix from PROC MIXED).
- Between group effect size vs. Quetiapine at each time point, calculated as the LS mean difference of each SEP-363856 group vs. Quetiapine at each time point divided by the model estimate of standard deviation, obtained as the square root of the corresponding diagonal element of the residual covariance matrix (R matrix from PROC MIXED).

In case the model above fails to converge, a spatial exponential covariance structure and a spatial power covariance structure along with an empirical sandwich estimator for the standard errors of the fixed effect parameters will be assumed sequentially. The first covariance structure to yield convergence will be used in the analysis. If the model fails to converge with all three structures specified above, the compound symmetry covariance structure will be assumed.

The normality and homoscedasticity assumptions underlying the primary MMRM model will be assessed graphically and included in the SAS outputs. Marginal studentized and Pearson-type residuals will be plotted against the predicted marginal mean values, respectively; the quantile-quantile (Q-Q) plots of these residuals versus the expected quantiles of the standard normal distribution will also be included in the SAS outputs to provide a graphical view of similarity and difference in the 2 distributions.

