15.3.5. Efficacy Analyses

Efficacy data will be summarized descriptively by treatment for the efficacy population.

The observed values of PANSS total score and subscale scores (positive, negative, and general psychopathology), CGI-S score, BNSS total score, MADRS total score, BACS composite score, ESS total score, SLOF total and subscale scores, EQ-5D-5L VAS, index score and dimension score, UPSA-B total score, and MSQ score, at Baseline and each scheduled post-Baseline visit, will be summarized descriptively. Changes from Baseline in these efficacy measures as well as changes from baseline in tobacco use and cotinine concentrations, will be summarized at each scheduled post- Baseline visit.

PANSS total score and CGI-S score data will also be summarized by age, sex, race, number of prior hospitalizations for treatment of schizophrenia, duration of schizophrenia, geographic region, and country.

The proportion of subjects who achieve a response, defined as a 20% or greater improvement (i.e. decrease) in PANSS total score from the Baseline, will be calculated for each scheduled visit and the Week 52 last-observation-carried-forward (LOCF). The proportion of subjects who achieve a response, defined as a 30% or greater improvement (i.e. decrease) in PANSS total score from the Baseline, will be summarized similarly. As exploratory analyses, PANSS total score and subscale scores, CGI-S score, BNSS total score, and MADRS total score will be analyzed using a mixed model for repeated measures (MMRM) under the missing-at-random (MAR) assumption. Under this assumption, the efficacy outcome of subjects in each treatment group after early discontinuation will exhibit the same future evolution as subjects in the same group remaining in the study. The MMRM model will include fixed factors for treatment, visit as a categorical variable, country, and treatment-by-visit interaction, and include Baseline score as a covariate. An unstructured covariance matrix will be used to model the within-subject correlation. Kenward-Roger approximation will be used to calculate the denominator degrees of freedom. The main estimator of the efficacy estimand is the least squares (LS) mean difference in each score change from Baseline at Week 52 from the analysis model of observed repeated measures data.

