16.1.1.3. Supplementary Analyses of PANSS Total Score

- Analysis of covariance

Change from Baseline in PANSS total score at each scheduled visit and at the LOCF endpoint will be analyzed using an analysis of covariance (ANCOVA) model. The model will include factors for treatment and country, and include Baseline PANSS total score as a covariate. The LS mean of each treatment group, LS mean differences (SEP-383656 vs. Quetiapine), their standard errors and two-sided 95% CIs, and the nominal p-values for treatment differences will be obtained from the model.

Based on the ANCOVA analysis, within group effect size at a given time point will be calculated as the LS mean of the treatment group divided by the standard deviation, obtained as the standard error of the LS mean multiplied by the square root of the treatment group sample size at that time point. Between group

Document: CCI

Author: PPD

Version Number: 0.6

Version Date: 30JAN2023

Template No.: CS_TP_BS016 Revision 6

Reference: CS_WI_BS005

Effective Date: 02Dec2019

effect size at a given time point will be calculated as the LS mean difference of SEP-363856 vs. Quetiapine divided by the pooled standard deviation, obtained as the standard error of the LS mean difference divided by the square root of the sum of inverse treatment group sample sizes at that time point.

Baseline PANSS total score will also be analyzed by an ANCOVA model including factors for treatment and country. The nominal p-values for treatment differences will be obtained from the model.

- Complete case analysis

The complete case analysis will be performed on the subset of subjects in the efficacy population who completed the double-blind treatment period and have Week 52/Visit 17 PANSS total score data available within 9 days post the last dose. The MMRM analysis as described in [Section 16.1.1.1](#) will be performed on these subjects.

- Analysis on the PP population

The MMRM analysis as described in [Section 16.1.1.1](#) will be performed on the PP population to evaluate the efficacy of the treatment for these subjects.

- Analysis with missing PANSS item(s) imputed

Due to the use of electronic clinical outcome assessment (eCOA) technology and extensive data quality monitoring during the study, no partially completed PANSS assessments are expected. However, in the rare event of a partially completed PANSS assessment, missing PANSS item scores will be imputed as described below.

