16.1.1.4. Subgroup Analyses of PANSS Total Score

For each of the subgroup factors listed in [Section 7.5](#), change from Baseline in PANSS total score at Week 52 will be analyzed using the MMRM method. For the subgroup factors other than country, the MMRM model will include fixed effects for treatment, subgroup, visit, country, Baseline PANSS total

Document: CCI

Author: PPD

Version Number: 0.6

Version Date: 30JAN2023

Template No.: CS_TP_BS016 Revision 6

Reference: CS_WI_BS005

Effective Date: 02Dec2019

score, and treatment-by-subgroup, treatment-by-visit, subgroup-by-visit, and treatment-by-subgroup-by-visit interactions. For the subgroup factor of country, the MMRM model will include fixed effects for treatment, country, visit, Baseline PANSS total score, and treatment-by-country, treatment-by-visit, country-by-visit, and treatment-by-country-by-visit interactions.

Subgroups that do not have at least 2 EFF population subjects with change from Baseline in PANSS total score data available at Week 52/Visit 17 in each of the two treatment groups will be excluded from the analysis.

Estimates obtained from the MMRM model will be presented separately for each subgroup. The nominal p-value for the treatment-by-subgroup interaction at Week 52/Visit 17 will be presented. The presence of a significant interaction effect will be assessed at the 0.10 level for homogeneity of the treatment effect across the different categories of a subgroup factor. In case of a significant interaction effect, estimates by subgroup will be examined to determine the nature of the interaction (qualitative or quantitative). The MMRM results of all subgroup analyses will also be presented using forest plots.

The observed PANSS total score and the change from Baseline values will also be summarized descriptively by treatment group and visit for each subgroup.

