17.6.3 BARNES AKATHISIA RATING SCALE (BARS)

The BARS is a rating scale geared toward assessment of neuroleptic-induced akathisia, though it can be used to measure akathisia associated with other drugs as well. The BARS consists of four items, including one item assessing objective restlessness (item 1), two items targeting subjective restlessness

Document: CCI

Author: PPD

Version Number: 0.6

Version Date: 30JAN2023

Template No.: CS_TP_BS016 Revision 6

Reference: CS_WI_BS005

Effective Date: 02Dec2019

(awareness and related distress; items 2 - 3), and one global clinical assessment of akathisia item (item 4). The objective and subjective items are anchored and utilize a 4-point scale. The global assessment item has a 6-point scale (from absence of akathisia through severe akathisia).

The BARS total score is the sum of items 1 through 3 and ranges from 0 to 9. Higher values of the BARS total score indicate higher severity of akathisia. If one or more of items 1 to 3 are missing at a visit, the BARS total score will be set to missing for that visit.

The post-Baseline BARS Global Clinical Assessment of Akathisia responses will be classified as 'worsened', 'unchanged', or 'improved', relative to a subject's Baseline response to this item. A higher score than that of the Baseline would be classified as 'worsened'. Conversely, a lower score would be classified as 'improved'. If the score is equal to that of Baseline, the score will be classified as 'unchanged'.

BARS is assessed at these study visits: Visit 2, Visit 3, Visit 5, Visit 10, and Visit 17.

Change from Baseline in BARS total score at each scheduled visit (Week 1/Visit 3, Week 4/Visit 5, Week 24/Visit 10, Week 52/Visit 17) will be analyzed using an MMRM similar to the model described in [Section 16.1.1.1](#) with Baseline BARS total score as the covariate. In addition, the MMRM analysis will be performed for subgroups of subjects based on whether the subject took concomitant medications for treatment of movement disorders during the study, which is similar to the model described in [Section 16.1.1.4](#).

Change from Baseline in BARS total score at each scheduled visit (Week 1/Visit 3, Week 4/Visit 5, Week 24/Visit 10, Week 52/Visit 17) will be analyzed using an ANCOVA model similar to the model described in [Section 16.1.1.3](#) (Analysis of covariance (including LOCF)) with Baseline BARS total score as the covariate.

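### The MMRMs use a single Baseline slope for all visits; if that slope drifts by Week 52, precision and the within-arm LS means suffer modestly, and a Baseline-by-visit term would prevent this at almost no cost

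*SAP*

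**What the plan says.** SAP 16.1.1.1 models change from Baseline in PANSS total score with fixed factors for treatment and "visit (Weeks 1, 4, 8, 16, 24, 32, 40, 48, 52; as a categorical variable", followed by "country, and treatment-by-visit interaction and include Baseline PANSS total score as a covariate". On covariance it states: "An unstructured covariance matrix will be used to model the within-subject correlation". Protocol 15.3.5 has the same structure: "country, and treatment-by-visit interaction, and include Baseline score as a covariate". The two documents agree; neither includes a Baseline-by-visit interaction.

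Other analyses refer back to this model: PANSS subscales, Marder and UPSM factors, CGI-S, BNSS, MADRS, BACS, ESS, SLOF, UPSA-B, AIMS, BARS and SAS. For BARS, SAP 17.6.3 keeps the same form, "with Baseline BARS total score as the covariate".

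The subgroup models in SAP 16.1.1.4 do let other covariates vary over time. The country model has "treatment, country, visit, Baseline PANSS total score, and treatment-by-country, treatment-by-visit, country-by-visit, and treatment-by-country-by-visit interactions", but Baseline again enters once.

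SAP 16.1.1.3 adds a supplementary analysis: "Change from Baseline in PANSS total score at each scheduled visit and at the LOCF endpoint will be analyzed using an analysis of covariance" model. Fitted visit by visit, it has its own Baseline slope at Week 52.

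**The concern.** The outcome is change from Baseline over a year. Its slope on Baseline at a given visit depends on how strongly that visit's score still correlates with Baseline, and on the spread of scores at that visit. Both can move between Week 1 and Week 52. A single slope cannot then fit both ends, and an unstructured covariance gives most weight to the early visits, where residual variance is smallest.

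Three Week 52 results are exposed:

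- the contrast, because Baseline variation left in the residual widens its interval;
- the effect sizes, which divide by the Week 52 residual SD;
- each arm's LS mean. Subjects who leave early are projected to Week 52 partly through the Baseline slope, so a wrong slope matters when dropout depends on Baseline or on the current score.

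**Working it through.** **Inputs from the documents.** Nine post-Baseline PANSS visits; unstructured covariance; 300 subjects randomized 2:1; about 80 expected one-year completers on SEP-363856 (Protocol 15.1). Implied retention: 300 × 2/3 = 200, and 80/200 = 40%. No SD, Baseline correlation, standard error or power is stated for any MMRM contrast, so there is no plan figure for the contrast to reproduce.

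**Assumptions.** Baseline SD (SD0) 9 or 12; Week 52 SD 9 to 14; correlation with Baseline at Week 52 (ρ) of 0.60, 0.45 or 0.20.

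**Step 1: slope of change on Baseline at visit j.** b_j = ρ_j × SD_j / SD0 − 1. With SD0 = 9 and Week 52 SD = 14:

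- ρ = 0.60: 0.60 × 14/9 − 1 = −0.07
- ρ = 0.45: 0.45 × 14/9 − 1 = −0.30
- ρ = 0.20: 0.20 × 14/9 − 1 = −0.69

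A rising SD offsets a falling correlation, so drift is possible but not certain.

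**Step 2: the common slope.** With residual covariance C and complete data, maximum likelihood gives g = 1′C⁻¹b / 1′C⁻¹1. This stays close to the early slopes, as the fitted values in the Step 4 table show.

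**Step 3: complete-data cost at Week 52.** Variance inflation = 1 + (b52 − g)² × SD0² / C52, with C52 = SD52² × (1 − ρ²). Using the fitted g from Step 4, SD0 = 9 and SD52 = 14:

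- ρ = 0.45: C52 = 196 × 0.7975 = 156.3. The gap is 0.30 − 0.06 = 0.24, and 0.24² × 81 = 4.7. Inflation is 1.03, so the SE is 1.5% larger.
- ρ = 0.20: C52 = 196 × 0.96 = 188.2. The gap is 0.69 − 0.07 = 0.62, and 0.62² × 81 = 31.1. Inflation is 1.17, so the SE is 8% larger.

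The implied residual SDs, √(156.3 + 4.7) = 12.7 and √(188.2 + 31.1) = 14.8, match the simulated 12.68 and 14.80.

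**Step 4: with dropout.** 2,000 simulated trials per row; 300 subjects at 2:1; four countries; no treatment effect; monotone MAR dropout depending on the current score, the same in both arms; 40% target retention. Both models were fitted by maximum likelihood with unstructured covariance. SEs are empirical, for the Week 52 contrast.

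| Drift | SD0 | SD52 | ρ at Wk 52 | Slope Wk 1 | Slope Wk 52 | Fitted common slope | SE, common | SE, Baseline-by-visit | Ratio |
|---|---|---|---|---|---|---|---|---|---|
| None | 9 | 9 | 0.60 | −0.40 | −0.40 | −0.40 | 1.236 | 1.238 | 0.998 |
| Mild | 9 | 14 | 0.60 | −0.09 | −0.07 | −0.06 | 1.881 | 1.882 | 0.999 |
| Mild | 9 | 11 | 0.60 | −0.13 | −0.27 | −0.13 | 1.497 | 1.491 | 1.004 |
| Moderate | 9 | 14 | 0.45 | −0.06 | −0.30 | −0.06 | 2.147 | 2.123 | 1.011 |
| Moderate | 9 | 11 | 0.45 | −0.10 | −0.45 | −0.13 | 1.737 | 1.686 | 1.030 |
| Moderate | 12 | 14 | 0.45 | −0.11 | −0.47 | −0.14 | 2.199 | 2.121 | 1.037 |
| Strong | 9 | 14 | 0.20 | −0.04 | −0.69 | −0.07 | 2.582 | 2.439 | 1.059 |
| Strong | 12 | 14 | 0.20 | −0.09 | −0.77 | −0.14 | 2.660 | 2.419 | 1.100 |

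At 30% and 60% target retention the strong-drift ratio (SD0 = 9) is 1.057 and 1.058. Mean contrasts were within about 0.06 points of zero for both models.

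**Step 5: effect size.** The Week 52 residual SD is 12.68 against 12.39 under moderate drift and 14.80 against 13.58 under strong drift (SD0 = 9, SD52 = 14). For a given contrast the reported effect size shrinks by 1 − 12.39/12.68 = 2% and by 1 − 13.58/14.80 = 8%.

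**Step 6: chance Baseline imbalance.** With SD0 = 9, the SE of the arm difference in mean Baseline is 9 × √(1/200 + 1/100) = 1.1, so a 1-point imbalance is ordinary. It is mis-adjusted by the slope gap: 0.24 points (moderate) or 0.62 points (strong).

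**Step 7: within-arm LS means.** Large-sample fits at about 40% retention, with MAR dropout depending on Baseline or the current score, put the common-slope Week 52 LS mean off by about 0.6 to 0.7 points when the correlation falls from 0.90 to 0.45. Under stronger decay the error is about 1.4 to 1.9 points. With Baseline-by-visit it is within about 0.1 point.

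**Step 8: does the visit-wise ANCOVA fill the gap?** Its observed-case SE at Week 52 was 2.274 under moderate drift (common-slope MMRM 2.147, Baseline-by-visit 2.123) and 2.551 under strong drift (2.582 and 2.439), both with SD0 = 9 and SD52 = 14. It exceeded the Baseline-by-visit MMRM in every scenario.

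**The case against.** The strongest reply is that this is a modelling preference with small consequences. One Baseline covariate is a legitimate prespecified choice, consistent between protocol and SAP. Efficacy is exploratory, p-values are nominal, the sample size rests on clinical considerations, and the primary endpoint is adverse-event incidence. All of that stands and is why the severity is low.

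Drift is also not shown. Baseline PANSS is capped at 80 by eligibility and later scores are not, so a rising SD is plausible and could leave the slope almost flat. This stands too: a reader might infer that precision is certainly lost, and the documents do not support that.

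Three other stronger readings go too far.

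- **All MMRMs start at Week 1.** They do not. BACS, SLOF and UPSA-B have only Weeks 12, 24 and 52, and ESS only Weeks 24 and 52. They share the single slope, but the early-visit cost was not computed for them.
- **A large loss of precision.** The complete-data formula alone, with correlation falling linearly from 0.85 to 0.30 at constant SD, gives variance +24% (SE +11%). With correlation falling from 0.90 to 0.45 and SD rising linearly from 9 to 14, it gives variance +2%. The larger figure depends on an assumed steep path and ignores the dropout that the plan expects.
- **A biased treatment contrast.** With the same dropout mechanism in both arms the error cancels. It need not cancel if dropout differs: with assumed retention of about 63% and 35%, the two models' contrasts differ by 0.4 points (moderate drift) to about 1 point (strong). The documents give no arm-specific dropout, so this is only a possibility.

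Finally, the ANCOVA does supply a Week 52 slope. It uses observed cases or LOCF rather than the MAR likelihood, so it answers the point only in part.

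**Conclusion.** The point holds as a low-severity improvement. No MMRM in the SAP has a Baseline-by-visit term. For scales measured from Week 1 (PANSS and its subscales and factors, CGI-S, BNSS, MADRS, AIMS, BARS, SAS) the common slope is set mainly by early visits. The cost is conditional on drift: none if the slope is stable, a few percent of the standard error in the middle of the assumed range, and up to about 10% at its far end. The LS-mean shift of about 0.5 to 2 points is the more noticeable effect, because SAP 16.1.1.1 reports each arm's LS mean and effect size under MAR.

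Every magnitude rests on assumed SDs, correlations and dropout. The simulations used maximum likelihood rather than REML with Kenward-Roger, which should hardly change the ratios.

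**What to change.** Add a Baseline-by-visit interaction to the MMRM in SAP 16.1.1.1, to the subgroup models in 16.1.1.4, and to each other model that refers to 16.1.1.1. Record it in SAP 3.7, since it departs from Protocol 15.3.5.

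The cost is one model term: 9 visits − 1 = 8 degrees of freedom for PANSS, and fewer for scales with fewer visits. When the slope is constant there is essentially no penalty (SE 1.238 with the term, 1.236 without). The visit-wise ANCOVA can stay as a supplementary analysis.
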